8.3 STANDARD COMPARISON METHODS

8.3.1 Primary and secondary endpoint analyses

Continuous endpoints with multiple post-baseline assessments will be analyzed using mixed-effects models for repeated measures (MMRM). Models will include terms for treatment group, visit,

treatment group by visit interaction, baseline value, baseline value by visit interaction, stratification category (FSHD repeat number category: FSHD 1, 1-3; FSHD 1, 4-9; FSHD 2; see 8.2), and region (North America, Europe). An unstructured covariance matrix will be used to model the correlations between repeated measurements within each patient. If the unstructured covariance matrix results in a lack of convergence, the first-order autoregressive covariance structure followed by the compound symmetric covariance structure will be used. The Kenward-Roger approximation will be used to estimate denominator degrees of freedom [2, 3]. Windowing (see 9.5.1) will be applied to ensure no more than one measurement per target visit window, per patient. Least-square (LS) mean, standard error, 2-sided 95% CI, and a 2-sided within-group p-value will be presented for each treatment group, at each visit. The difference in LS means between treatment groups (Losmapimod 15 mg BID – Placebo BID), the 2-sided 95% CI of the difference, and a 2-sided p-value will be presented at each visit.

In addition, certain continuous endpoints with multiple post-baseline assessments will be analyzed using a linear mixed-effects model (LME, see 10.2). In these models the response variable is the absolute measurement, at baseline and post-baseline assessments. Models will include terms for treatment group, time, treatment group by time interaction, FSHD repeat number category (FSHD 1, 1-3; FSHD 1, 4-9; FSHD 2; see 8.2), and region (North America, Europe). Intercept and time will be fitted as random effects. In this model, 'time' is time from first dose normalized over the treatment period of 48 weeks (335 days). It is derived as follows:

$$\text{Time} = (\text{Assessment/event date} - \text{Date of first dose}) / 335$$

[figure not shown]

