The treatment effect will be assessed over the entire treatment period (i.e., 48 weeks) for each treatment group. Data to be included (scheduled and unscheduled) will be selected through windowing. An unstructured covariance matrix will be used to model the correlations between repeated measurements within each patient. If the unstructured covariance matrix results in a lack of convergence, the first-order autoregressive covariance structure followed by the compound symmetric covariance structure will be used. LS mean, SE and 2-sided 95% CI for the slope and intercept, and a 2-sided p-value for the slope, will be presented for each treatment group. The difference in LS mean slopes between treatment groups (Losmapimod 15 mg BID – Placebo BID), the 2-sided 95% CI of the difference, and a 2-sided p-value will be presented. In addition, the average percentage change per year (annualized percentage change) will be presented for each treatment group. This is derived as $[(\text{slope}/\text{baseline}) * (365/335) * 100]$, where baseline is the LS mean intercept, slope is the LS mean slope and 335 is the planned duration of treatment with study drug in days minus 1. The difference in average percentage change per year between treatment groups (Losmapimod 15 mg BID – Placebo BID) will also be presented.

Least squares means derived from the MMRMs will be plotted over time for both treatment groups with error bars showing standard errors. Annualized percentage changes estimated from LMEs will be presented as line charts.

For all MMRMs and LMEs fitted, model assumptions will be checked by examining plots of residuals. Given the sample size of the study and the nature of the variables investigated, the central limit theorem (CLT) is highly likely to guarantee that the analysis of means is appropriate. However, if the

distributions of the data strongly imply the CLT isn't appropriate, the analysis may rely on nonparametric methods or transformations of the data.

In the case that a model does not converge under any of the three covariance structures, analysis will consist of descriptive statistics only.

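### The supportive linear mixed model gives each arm its own baseline mean and its own %/year denominator, so the %/year difference picks up chance baseline imbalance and is reported without a confidence interval

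*SAP*

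**What the plan says.** SAP 8.3.1 describes two models for continuous endpoints with repeated assessments.

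- **MMRM (primary).** It models change from baseline and adjusts for baseline; its terms include "treatment group by visit interaction, baseline value, baseline value by visit interaction".
- **LME (additional).** Here "In these models the response variable is the absolute measurement, at baseline and post-baseline assessments". On fixed effects: "Models will include terms for treatment group, time, treatment group by time interaction, FSHD repeat number category", plus region. No baseline covariate is listed. On random effects: "Intercept and time will be fitted as random effects". Time is days from first dose divided by 335.

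The LME outputs for each arm are "LS mean, SE and 2-sided 95% CI for the slope and intercept". The slope difference gets an interval and a test: "the 2-sided 95% CI of the difference, and a 2-sided p-value will be presented. In addition, the average percentage change per year" follows in the next sentence. The annualised % change for each treatment group is (slope/baseline) × (365/335) × 100, "where baseline is the LS mean intercept". "The difference in average percentage change per year between treatment groups" is to be presented as well, but no SE, CI or p-value is named for it.

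SAP 10.2.1.1 makes the MMRM the primary analysis of the primary endpoint and adds the LME. SAP 10.2.2.2 and 10.2.2.4 do the same for B-muscle MFI and Neuro-QoL-UE. Protocol 9.1.6.3 plans differences in slopes and in % change per year but does not list the LME's terms.

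**The concern.** Randomisation makes the two time-0 means equal in expectation. A model that keeps baseline as a response and also fits a treatment main effect estimates those means separately, so it gives up part of the baseline information that the MMRM uses.

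The %/year scale adds a second effect. The LS mean intercept is reported by arm and the annualised change is computed by arm, so the natural reading is that each slope is divided by its own arm's intercept. Two arms losing reachable workspace at the same absolute rate then show different %/year values whenever their baselines differ by chance. The slope difference and the %/year difference come from one model and could point in opposite directions.

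The %/year contrast is a planned output, and the annualised changes are plotted. As written, its reader would have no measure of its uncertainty.

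**Working it through.** **The plan's own figure.** The SAP gives no figure for the LME. Its power statement (SAP section 5) reproduces: 105 per arm less 10% is 94.5; noncentrality = 0.05/(0.08 × √(2/94.5)) = 4.30; power = 99.0%. The stated minimum of 95% therefore holds. The planned treatment length also agrees: 48 × 7 - 1 = 335.

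**Inputs.** From the SAP: 105 per arm, SD of change 0.08, visits at baseline and Weeks 4, 12, 24, 36 and 48 (days 0, 28, 84, 168, 252, 335 from first dose), and the 365/335 formula. Assumed, because the documents do not give them: baseline mean 0.5, intercept SD 0.12-0.25, residual SD 0.05, slope SD 0.04 per 48 weeks, intercept-slope correlation -0.5 to +0.3, complete data. These match the SAP's SD of change: √(2 × 0.05² + 0.04²) = 0.081.

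**1. Slope difference, separate intercepts.** With t = day/335, Σ(t - t̄)² = 0.771.

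Variance = (2/105) × (0.04² + 0.05²/0.771) = (2/105) × 0.00484 = 0.0000922, so SE = 0.0096.

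**2. Slope difference, common time-0 mean.** Generalised least squares with V = ZGZ' + σ²I and no treatment main effect gives:

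| Intercept-slope correlation | SE, separate | SE, common | Excess variance, separate over common |
|---|---|---|---|
| 0 or +0.3 | 0.0096 | 0.0095-0.0096 | 0-3% |
| -0.3 | 0.0096 | 0.0091-0.0093 | 7-12% |
| -0.5 | 0.0096 | 0.0086-0.0089 | 15-24% |

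Ranges run over the intercept SD.

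**3. The interval that is not reported.** Ignoring error in the denominator, the SE of the %/year difference is (0.0096/0.5) × (365/335) × 100 = 2.09 points. Allowing for the own-arm intercepts by the delta method, with a slope of -0.03 in both arms, gives 1.97-2.18. The 95% half-width is 1.96 × 1.97 to 1.96 × 2.18, or 3.9 to 4.3 points/year.

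**4. Denominator effect alone.** Take the same slope, -0.03 per 48 weeks, in both arms, with baselines 0.47 and 0.53.

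- Arm 1: (-0.03/0.47) × (365/335) × 100 = -6.95 %/year
- Arm 2: (-0.03/0.53) × (365/335) × 100 = -6.17 %/year
- Spurious difference: -0.79 points/year

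At an assumed baseline SD of 0.2, the SE of the imbalance is 0.2 × √(2/105) = 0.0276, so 0.06 is 2.2 SE. A 1-SE imbalance gives about (0.03/0.5²) × 0.0276 × 108.96 = 0.36 points/year.

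**5. Agreement of the two contrasts.** In a separate simulation (115 per arm, SD of change 0.08, baseline SD 0.15, baseline mean 0.4-0.6, decline of 0.05 per 48 weeks in both arms), the slope difference and the %/year difference had opposite signs in 5-9% of runs. With a common intercept, the correlation between the %/year difference and baseline imbalance was about 0.

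**The case against.** The strongest reply is that no decision rests on this model. The MMRM is primary for the reachable-workspace endpoint, MFI and Neuro-QoL-UE and adjusts for baseline; the LME is not a step in the sequence of SAP 2.4.2. A random intercept-and-slope model with arm-specific intercepts is a standard specification, and its slope contrast is unbiased over randomisation. All of this stands and limits the weight of the point.

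The efficiency loss depends on an intercept-slope correlation that the documents do not give; at 0 or +0.3 it is negligible. That also stands. A reader might infer losses of up to 35%, or an SE of 2.5 points/year, from larger slope SDs. Those need an SD of change of about 0.107 and 0.093 respectively, which the SAP's 0.08 does not support.

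The 0.8-point example is unfavourable. Inclusion criterion 4 limits unweighted dominant-arm Q1-Q4 RSA to 0.2-0.7. A uniform spread over that range has SD 0.144, at which the example is a 3.0-SE imbalance. The endpoint is a different measure, so this is only indicative. Even 0.8 is small beside ±4.

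On the missing interval, SAP 8.1 allows CIs where appropriate and the table shells are not available, so one may yet be shown. But 8.3.1 names an interval for the slope difference and none for this one, and no method is given for a difference of two ratios.

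**Conclusion.** The point holds as a minor improvement to a supportive analysis. The missing interval, about ±4 points/year, matters most. The denominator effect is real but modest, and the precision gain ranges from nil to 24% of variance according to the assumed correlation. The own-arm denominator is the natural reading of 8.3.1, not an explicit statement.

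Two stronger readings are tempting and are not supported:

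- That the slope test is biased or the primary result at risk. The slope contrast is unbiased over randomisation. The issues are precision and, in a given trial, sensitivity to chance imbalance.
- That the protocol already quotes a between-arm %/year contrast from Phase 2, -0.62 versus -7.49. Protocol 1.2.4 sets each group's extension-period figure against its own first-year figure, for the dominant arm; it does not present those two numbers as a treatment comparison.

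The sizes rest on the assumed baseline mean, intercept SD, residual SD, slope SD and correlation listed in the working, and on complete data.

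**What to change.** In SAP 8.3.1:

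1. Drop the treatment main effect from the LME so that both arms share a time-0 mean. Keep time, treatment-by-time, FSHD category, region and the random effects.
2. Use that common intercept as the denominator of the annualised % change in both arms.
3. Report a 95% CI for the %/year difference, by the delta method or a bootstrap of patients, and say which.
4. Keep actual assessment dates for time. For pre-dose values, including the screening MRI, set only the treatment-by-time term to zero, i.e. enter treatment × max(time, 0).

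Step 4 is better than moving the screening scan to day 0. Protocol 4.2 may spare a rescreened patient a repeat MRI if the scan is less than 60 days old at treatment start. Re-dating such a scan would assign up to about 395 days of change to 335 days, overstating that patient's rate by up to about 18% (395/335 = 1.18).

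The cost is SAP wording and minor reprogramming of the LME for each endpoint that uses it. No new data are needed, and protocol 9.1.6.3 does not fix the LME's terms. The primary MMRM and the testing sequence stay as they are.

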8.3.3 Pharmacokinetic analyses

See 10.5.1 below.

8.4 STATISTICAL SIGNIFICANCE

See Section 2.4.2 for a summary of significance thresholds for the primary and secondary endpoints. All other statistical tests will be 2-sided and performed using a 0.05 significance level.

8.5 EXAMINATION OF SUBGROUPS

Subgroup analyses of the primary and secondary efficacy endpoints will be conducted. Subgroups to be analyzed are:

- Correct FSHD type 1 repeat categories 1-3; FSHD type 1 repeat categories 4- 9; FSHD type 2
- Baseline clinical severity score (Ricci score 2- 3 and 3.5- 4)
- Region (North America and Europe)
- Sex (Male and Female)
- Age (<45 years old and \geq 45 years old)
- Baseline weight (<77kg vs \geq 77kg)

The by-site analysis of the primary endpoint will also be performed.

Note: models will be fitted for all subgroups, but in the case of failure to converge due for example to small sample size, model results will not be presented.

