9.1.3. Sample Size Determination

The target population for this clinical trial is patients with FSHD1 and FSHD2. The clinical trial will reflect the current epidemiologic information about FSHD, with patients with FSHD1 making up approximately 95% of the study population and the other 5% being people living with FSHD2. However, all studies thus far have been conducted with FSHD1 patients; therefore, this calculation was based on that population. Additional FSHD2 patients will be enrolled to explore safety and efficacy in this subgroup.

Assuming the within-group SD of change is 0.08 and that 10% of the study population has missing Week 48 data, a sample size of 210 patients with FSHD1 (105 patients per group) will be needed to provide at least 95% power with a 2-sided test at 0.05 significance level to detect a difference of 0.05 between losmapimod and placebo in change from baseline in average total RSA Q1-Q5 with 500 g wrist weight at Week 48. An additional approximately 20 patients with FSHD2 will be recruited. The primary analysis will include patients with FSHD1 and FSHD2.

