2.4.2 Multiple testing strategy

To control the overall type I error rate, the primary endpoint and secondary efficacy endpoints will be tested in sequence as follows:

1. The primary endpoint will be tested at 2-sided significance level $\alpha=0.05$.
2. If a statistically significant result is obtained for the primary endpoint (test 1), change from baseline in WB longitudinal composite MFI in B muscles at Week 48 and relative change from baseline in average shoulder abductor strength by hand-held quantitative dynamometry at Week 48 will be tested using the Bonferroni procedure, i.e., each will be tested at 2-sided $\alpha = 0.025$ (test 2).
 - If both tests are significant, a statistically significant result is obtained from test 2. The remaining significance level from test 2 = 0.05.
 - If only one of the 2 tests is significant, a statistically significant result is obtained from test 2. The remaining significance level from test 2 = 0.025.
 - If neither test is significant, a statistically significant result is not obtained from test 2.
3. If a statistically significant result is obtained from test 2, PGIC at Week 48 will be tested at the remaining significance level from test 2 (test 3).
4. If a statistically significant result is obtained from test 3, change from baseline in Neuro-QoL-UE at Week 48 will be tested at the remaining significance level from test 3, which is equal to the remaining significance level from test 2.

In recognition of the complexities of this rare disease and the novelty of this research field, in case the result of the primary analysis (MMRM) of the primary endpoint is on the boundary of statistical significance, but at least one of the following is true:

- results from most sensitivity analyses are nominally significant,
- result of PGIC at Week 48 is nominally significant,
- result of Change from baseline in WB longitudinal composite MFI in B muscles at Week 48 is nominally significant,

AND

- results from most of the remaining secondary and exploratory efficacy endpoints are directionally favorable to losmapimod,

the totality of evidence will be utilized to support the decision making.

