5. SAMPLE SIZE CONSIDERATIONS

The target population for this clinical trial is patients with FSHD1 and FSHD2. The clinical trial will reflect the current epidemiologic information about FSHD, with patients with FSHD1 making up approximately 95% of the study population and the other 5% being people living with FSHD2.

Assuming the within-group standard deviation (SD) of change is 0.08, a sample size of 210 patients with FSHD1 (105 patients per group) will be needed to provide at least 95% power with a 2-sided t-test at 0.05 significance level to detect a difference of 0.05 between losmapimod and placebo for the primary endpoint. An additional approximately 20 patients with FSHD2 will be recruited. The primary analysis will include patients with FSHD1 and FSHD2. Premature withdrawal and missing data are discussed in 9.1.

For the secondary efficacy endpoints of change from baseline in WB longitudinal composite MFI of B Muscles and PGIC at Week 48, assuming the within-group SDs are 0.72 and 1.0 respectively, a sample size of 210 patients with FSHD1 will provide at least 95% power with a 2-sided t-test at 0.025 significance level to detect a difference of 0.5 and 0.6 respectively between losmapimod and placebo.

For the secondary efficacy endpoint of relative change from baseline in average shoulder abductor strength at Week 48, assuming the within-group SD is 46, a sample size of 210 patients with FSHD1 will provide at least 75% power with a 2-sided Wilcoxon rank-sum test at 0.025 significance level to detect a difference of 20.2 between losmapimod and placebo.

In the above calculations, the assumed treatment differences and SDs are based on results from an ongoing Phase 2 study, Study FIS-002-2019 (ReDUX4). It is also assumed that 10% of the study population has missing Week 48 data. All power calculations were performed using the POWER Procedure of SAS[®] Version 9.4.

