10.2 EFFICACY ANALYSES

Efficacy analyses are based on the FAS. The primary and secondary efficacy analyses will also be split by subgroup of the FAS.

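### Subgroup effects come from 13 separate fits with no treatment-by-subgroup contrast; one pooled exploratory model per factor would be a cheap improvement

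*SAP*

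**What the plan says.** SAP 8.5 plans subgroup analyses of the primary and secondary efficacy endpoints by six factors: FSHD type and repeat category (three levels), and Ricci score, region, sex, age and weight (two levels each). That makes 3 + 5 × 2 = 13 levels. The closing note begins "models will be fitted for all subgroups, but in the case of failure to converge" and goes on to withhold the model results in that case.

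The method is separate fits:

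- SAP 10.2: "The primary and secondary efficacy analyses will also be split by subgroup of the FAS".
- SAP 10.2.1.2 repeats the main analysis of SAP 10.2.1.1 in the subgroups.
- SAP 8.2 drops the repeat-category or region covariate when it defines the subgroup, which fits separate models rather than one model with an interaction.

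The interactions named in SAP 8.3.1 are treatment by visit and baseline by visit (MMRM) and treatment by time (LME). Each MMRM fit gives a treatment difference, a 95% CI and a p-value at each visit. SAP 8.4 sets the threshold outside the primary and secondary testing scheme: "All other statistical tests will be 2-sided and performed using a 0.05 significance level".

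SAP 8.2 adds a sparse-data rule. If a stratum (FSHD1 with 1-3 repeats, FSHD1 with 4-9 repeats, FSHD2) has fewer than five patients with data in either arm of an analysis, that stratum is left out of that analysis. If this happens in two of the three strata, all patients are kept and the stratum term is dropped.

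Protocol 9.1.5 leaves the subgroup methods to the SAP. Protocol 9.1.3 gives the reason for recruiting FSHD2: "Additional FSHD2 patients will be enrolled to explore safety and efficacy in this subgroup".

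**The concern.** A subgroup analysis asks whether the treatment effect differs between levels. The plan answers a different question in each level: whether the effect there differs from zero at 0.05. Each level has fewer patients than the trial, so a drug that works equally well everywhere can reach significance in one level and miss it in the other. With two p-values side by side and no contrast between them, readers are drawn to treat that pattern as heterogeneity.

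FSHD2 is the most exposed level, because about 20 patients cannot be expected to give a significant result even if they benefit fully. What is at stake is how the subgroup results are read and reported. The confirmatory result does not depend on them.

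**Working it through.** **Inputs.** SAP 5: SD of change 0.08, difference 0.05, 105 FSHD1 patients per group, and "It is also assumed that 10% of the study population has missing Week 48 data". SAP 3.1: about 230 patients, 1:1, of whom 20 have FSHD2. Assumed: the split of every factor other than FSHD type, and t-tests on change in place of the MMRM.

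**1. The plan's own figure.** Evaluable per arm: 105 × 0.9 = 94.5. SE = 0.08 × √(2/94.5) = 0.0116, and 0.05/0.0116 ≈ 4.30. Power ≈ Φ(4.30 − 1.96) = 99.0%, so the stated 95% or more is met. With FSHD2 included, 230 × 0.9 / 2 = 103.5 per arm and power is 99.4%.

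**2. Uniform effect, separate tests.** With n evaluable per arm in a level, SE = 0.08 × √(2/n), and power p comes from the noncentral t. The chance that exactly one of two levels is significant is p1(1 − p2) + p2(1 − p1).

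| Split | n per arm | Power at 0.05 | One level only, effect 0.05 | One level only, effect 0.04 |
|---|---|---|---|---|
| 50:50 | 51.75 / 51.75 | 88% / 88% | 21% | 41% |
| 60:40 | 62.1 / 41.4 | 93% / 80% | 24% | 43% |
| 70:30 | 72.45 / 31.05 | 96% / 68% | 34% | 51% |
| FSHD1 / FSHD2 | 94.5 / 9 | 99% / 24% | 76% | 78% |

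Example, 50:50: SE = 0.08 × √(2/51.75) = 0.0157, power 0.883, and 2 × 0.883 × 0.117 = 0.207. For FSHD2: SE = 0.08 × √(2/9) = 0.0377, power 0.239, and 0.990 × 0.761 + 0.239 × 0.010 = 0.756. The last row pools the two FSHD1 repeat categories, which SAP 8.5 reports separately.

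**3. Sensitivity to SD** (50:50, effect 0.05): 2% at SD 0.06, 10% at 0.07, 21% at 0.08, 41% at 0.10. The plan assumes only 0.08. A lower value stands for what baseline adjustment might achieve.

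**4. What an interaction test would do.** In 4,000 simulated trials per scenario with a uniform effect and five two-level factors treated as independent, a treatment-by-subgroup test was significant in about 5% per factor. Across five factors, at least one was significant in 21-24% of trials (1 − 0.95⁵ = 23%). Its power is limited. For a true difference of 0.05 between levels at 50:50, SE = 0.0157 × √2 = 0.0222 and power = Φ(0.05/0.0222 − 1.96) ≈ 61%. For FSHD type, SE = √(0.0116² + 0.0377²) = 0.0395 and power is about 24%.

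**5. The fewer-than-5 rule.** About 10 FSHD2 patients per arm are planned, or nine with Week 48 data. To keep FSHD2 in both levels of a two-level factor, each arm needs at least five in each level. Nine cannot do that, and ten can only if both arms split exactly 5:5. If every patient were equally likely to fall in either level, that chance is (252/1024)² = 0.246² ≈ 6%. FSHD2 patients will therefore usually drop out of at least one level, and the two levels may then hold different disease mixes. Exceptions are more FSHD2 recruits than planned, or a second sparse stratum, which switches the rule to keeping everyone. A whole-FAS model has 9-10 FSHD2 patients per arm and does not trigger the rule.

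**The case against.** The strongest reply is that the information is already there. SAP 8.3.1 requires the treatment difference and its 95% CI in every fit. The levels of a factor are different patients, so anyone can subtract the two estimates and combine their standard errors. This stands. A reader might infer that comparing significance is the only contrast the tables allow, and the documents do not support that. The table shells are in a separate file, so the layout is also unseen.

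A reader might also infer that the drug will look absent in one level. Non-significant is not absent: the level estimates stay unbiased. With a uniform effect of 0.05, the chance of a zero or negative estimate is 0.07% per level at 50:50 and about 9% in FSHD2.

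A third tempting reading is that the FSHD2 estimate will be lost to non-convergence. SAP 8.3.1 provides two simpler covariance structures first, and descriptive statistics if all three fail. Pooling the covariance would narrow the FSHD2 interval only slightly: half-width 2.12 × 0.0377 = 0.080 against 1.97 × 0.0377 = 0.074, about 7%. Even that assumes FSHD2 shares the FSHD1 variance, and the protocol says all studies so far were in FSHD1.

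Finally, the discordance rates rest on assumed splits and a raw SD, and an interaction test has low power. Both points stand and limit what can be claimed. Neither is a reason to leave the contrast out.

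**Conclusion.** The omission is confirmed in the public text: separate fits in 13 levels, a p-value in each, and no treatment-by-subgroup term or rule for reading the results. On the plan's SD and effect, a uniform benefit would show as significant in one level only in about 21-34% of trials for a factor split between 50:50 and 70:30, and in about 76% for FSHD1 against FSHD2. The first range depends on assumed splits and falls to about 2% at an even split with SD 0.06. The FSHD2 figure rests on the planned 20 patients and an FSHD1-based SD. The loss of FSHD2 patients through the fewer-than-5 rule follows from the planned numbers, with the exceptions noted.

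This is a worthwhile, cheap improvement and not a flaw in the confirmatory analysis. A reader might infer a threat to the primary result, but the subgroups lie outside the testing sequence in SAP 2.4.2 and its borderline-result provision does not name them.

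**What to change.** Before unblinding, amend SAP 8.5, 10.2 and 10.2.1.2 as follows.

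- **MMRM endpoints.** For each factor, fit one model on the whole FAS, adding subgroup, subgroup × visit, treatment × subgroup and treatment × visit × subgroup terms, with a common covariance. Report the Week 48 difference with 95% CI in each level, and the interaction estimate with 95% CI and an exploratory p-value.
- **Shoulder abductor strength (stratified Wilcoxon).** Report level-specific Hodges-Lehmann estimates with CIs and an exploratory between-level contrast.
- **Within-level p-values.** Omit them, or state that they are not evidence of heterogeneity.
- **Reading rule.** State that a non-significant interaction does not show homogeneity.

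The cost is a paragraph of SAP text and modest programming, with no new data. The pooled model assumes a common covariance and common covariate effects across levels. The interaction test has low power (about 61% at 50:50 and 24% for FSHD type, for an interaction of 0.05), so the estimate and its interval should carry the interpretation.
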